In the Delayed Monetary Reward Control group, participants will not be eligible to receive any performance-based rewards during the first 12 months, but will receive information on their toothbrushing performance. After the 12-month follow-up visit, the Control group participants will have the option to participate in a delayed 6-month open label extension to earn the same monetary rewards the intervention group was eligible to earn until Month 6. This is not a formal part of this trial, but rather a necessary condition of the trial design to assure that all participating parents/caregivers have the chance to earn the same monetary incentives. Control participants who choose the 6-month extension will follow the same procedures (i.e., texting notifications) as the Monetary Reward intervention group from the 12-month follow-up to an 18-month follow-up; they will be randomized into one of two groups which will convey weekly drawing information to participants either weekly or quarterly. At the 18-month follow-up visit, they will be able to collect the earned incentives when the child attends the visit and the returned TP pump is weighed.

After the Month 6 visit through the end of the trial (Month 12), participants will continue to sync their powered toothbrushes and will receive incentives for syncing, but will not be eligible to receive rewards for toothbrushing performance, to assess behavior maintenance after the rewards have ended.

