7.2.4 Month 12 Follow-Up Study Visit (Visit 5, T = business day 260 ± 28)

The Month 12 visit is the final study visit for participants randomized to the incentive group. During this visit, a trained staff member will complete the final questionnaire and post-test with the parent/caregiver.

- Administer CAPI questionnaire to parent/caregiver.
- Collect the TP pump. Record weight of TP pump.
- Record medical history and perform ASTDD BSS dental screening on child participant's teeth (by blinded dental provider); record decay and assess treatment urgency. Children with urgent treatment needs will be referred with a warm handoff to staff at the corresponding dental clinic.
- Apply plaque disclosing agent to child's teeth (by blinded dental provider).
- Take extraoral photograph(s) of the facial surfaces of child's anterior teeth.
- Brush off plaque disclosing solution.
- Apply FV to the child's teeth (by dental provider) (Continuing delayed control arm only).
- Give the parent/caregiver an electronic tablet to watch the Anticipatory Guidance presentation.
- Give the parent/caregiver the accumulated rewards (*Intervention Group*).
- Distribute 1 new toothbrush head and new TP pump.
- Dispense syncing payments to the parent/caregiver (*both groups*).
- Give the parent/caregiver \$30 compensation for attending this 12-month visit.
- After this visit, perform FGDs.
- *Optional for Control Group only:* Randomize Control Group participants who want to continue into 1 of 2 groups: weekly or quarterly drawing result communication. Explain the intervention procedures and Monetary Rewards program to the parent/caregiver and have her/him explain it back in her/his own words (teachback). Schedule the family's next visit (in approximately 3 months).

7.2.5 Month 15 Follow-Up Study Visit (*Optional for Control Group Only, Visit 6, T = business day 325 ± 28*)

During this Month 15 follow-up visit, the following procedures will be completed by trained staff members.

- Administer CAPI questionnaire to parent/caregiver.

- Dispense new toothbrush head.
- Dispense earned rewards to the parent/caregiver.
- Dispense syncing payments to the parent/caregiver.
- Schedule the family's next visit (in approximately 3 months) and give the parent/caregiver \$30 compensation for attending the 15-month visit.

7.2.6 *Month 18 Follow-up Study Visit (Optional for Control Group Only, Visit 7, T = business day 390 ± 28)*

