12.2 Sample Size Considerations

With 2 parallel groups, the sample size calculation was conservatively conducted for one continuous outcome using short-term pilot data; the mean number of qualifying brushing episodes in a half-day window per week through 6 weeks was 5.5 with a standard deviation (SD) of 4.8 for a coefficient of variation (CV) of 0.87. To be more conservative, a SD 25% larger (i.e. 6.0) was used. The mean percent of qualifying brushing episodes (out of 14 half-days per week) was 63% with a SD=32% for a CV=0.514. A sample size of 91 in each group is estimated to have 84% power to detect a difference in means of 2.65 with a common SD of 6.0 using a two group t-test with 2-sided alpha=0.05.

In addition, a sample size of 91 in each group was estimated to have 85% power to detect a 1.25-fold change in means (expected ratio) between intervention and control with the larger (more conservative) CV=0.525 using a two group 2-sided t-test with alpha=0.05. With a CV=0.567 and a 1.25-fold change or a CV=0.695 and a 1.30-fold change, n=91 per group is still estimated to have 80% power.

Assuming 75% retention over 12 months, a total of 244 parent-child dyads (N=488) will need to be enrolled. (Retention was 85% over 24 months in the team's recently completed glass ionomer sealant and fluoride varnish trial (GIFT) in a similar

population. Retention was 75% over 2 months in the BEECON pilot trial, but retention procedures have been added including a 2 week run-in to eliminate people enrolling only for the powered toothbrush.)

Sample sizes for semi-structured interviews and focus group discussions are based on prior experience. Focus group discussions with a total of 40 parent/caregiver participants are expected to reach saturation, but it is possible an additional focus group discussion will be needed to reach saturation.

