12.4 Final Analysis Plan

Intent-to-treat (ITT) analyses standard in incentive based behavioral economics studies will be utilized (e.g. Halpern *et al.* 2015, Patel *et al.* 2016). Generalized linear mixed models (GLMMs) will be used to compare primary and secondary outcomes over time between groups. GLMMs make fewer missing data assumptions than other methods, which assume missing data are missing completely at random. Identity link will be used for numeric (interval) outcomes (e.g., mean number of qualifying half-day toothbrushing episodes per week, through Month 6 visit; mean OHI-MIS plaque score; and TP pump weight change). The group x time interaction will also be assessed; short-term effects will be assessed for 1 month of the intervention, mid-term effects after the novelty effect of powered toothbrushing usually ends for the Month 3 Visit, and long-term effects for the Month 6 Visit (primary outcome), as well as, maintenance of behavior after removing the incentives for the Month 12 Visit. Recent, powerful Precision Medicine methods which do not inflate Type I error will be used to detect heterogeneity of treatment effects by groups of participants based on baseline characteristics (e.g., Lazar *et al.* 2013). Multiple imputation using chained equations (MICE) for arbitrary missingness patterns (Raghunathan *et al.* 2001; van Buuren 2007) will be used for sensitivity analyses. Supplemental analyses will also explore: a) trajectories of mean number of qualifying half-day brushing episodes per week over time; as well as b1) variability in morning brushing times, b2) variability in evening brushing times, and c) variability in weekday versus weekend brushing times associated with mean number of qualifying half-day brushing episodes, OHI-MIS plaque scores, and ASTDD BSS caries screening measures.

To examine potential impact of timing of drawing reward communication time, GLMM analyses as above will be performed comparing the weekly and quarterly drawing result communication arms for primary and secondary outcome data from Month 12 to Month 18.

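### The Month 12-18 weekly-versus-quarterly comparison has no stated covariate for brushing before the second randomisation; prespecifying the Month 6-12 mean would be a near-free gain in precision

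*Combined protocol and SAP*

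**What the plan says.** Section 7.2.4 sets up a second randomisation at the Month 12 visit: "Randomize Control Group participants who want to continue into 1 of 2 groups: weekly or quarterly drawing result communication". Section 6.1 repeats it: "they will be randomized into one of two groups which will convey weekly drawing information to participants either weekly or quarterly". Entry is optional. Section 4 keeps the weekly drawings, amounts and probabilities the same in both groups, so that only the timing of the results differs.

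The analysis is one sentence of section 12.4: "GLMM analyses as above will be performed comparing the weekly and quarterly drawing result communication arms", applied to primary and secondary outcomes between Month 12 and Month 18. The model referred back to is a generalised linear mixed model (GLMM) comparing groups over time, with a group-by-time interaction. Neither place names a baseline or prior-outcome covariate.

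Brushing before this randomisation is recorded. For the period from Month 6 to Month 12, section 6.1 says "participants will continue to sync their powered toothbrushes and will receive incentives for syncing", and section 3.2.2 lists mean weekly qualifying episodes over that interval as a secondary outcome. The plaque photograph is taken at the same Month 12 visit (7.2.4).

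Section 12.2 gives no sample size, effect or power for weekly versus quarterly. Section 6.1 places the extension outside the formal trial.

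**The concern.** The second randomisation has its own baseline, namely what each dyad was doing just before Month 12. As written, the data window starts at Month 12, so earlier brushing has no stated role, either as a covariate or as an earlier time point. A dyad random effect would not replace it. Fitted to Month 12-18 weeks only, it models correlation among those weeks but does not remove stable between-dyad differences from the group contrast. A covariate added only to the main reward-versus-control model would not reach this analysis either.

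Precision is at stake. The comparison draws only on controls who are still in the trial at Month 12 and choose to continue, so it is small and its size cannot readily be increased. Naming the covariate in advance also removes a later choice between adjusted and unadjusted results.

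**Working it through.** **Inputs from section 12.2.** The SD comes from "To be more conservative, a SD 25% larger (i.e. 6.0) was used" (pilot 4.8 x 1.25 = 6.0), and alpha is 0.05 two-sided ("common SD of 6.0 using a two group t-test with 2-sided alpha=0.05"). Enrolment: "Assuming 75% retention over 12 months, a total of 244 parent-child dyads (N=488) will need to be enrolled".

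**Inputs not in the documents, so assumed.** 1:1 allocation; uptake of 100%, 75% or 50%; rho of 0.3, 0.5 or 0.7 (the within-arm correlation of a dyad's Month 6-12 mean with its Month 12-18 mean); true difference of 2.65, 1.5 or 1.0 episodes per week. The 2.65 is borrowed from the reward-versus-control calculation and is not a target for this comparison.

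**Step 1: reproduce the plan's figure.** The plan states: "A sample size of 91 in each group is estimated to have 84% power to detect a difference in means of 2.65". The noncentrality is 2.65 / (6.0 x sqrt(2/91)) = 2.98 on 180 degrees of freedom, and noncentral-t power is 84.2%. The stated 84% reproduces.

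**Step 2: size of the second comparison.** 244 / 2 = 122 controls, and 122 x 0.75 = 91.5 retained. Per arm:
- 100% uptake: about 45
- 75% uptake: 91.5 x 0.75 / 2 = 34
- 50% uptake: 91.5 x 0.50 / 2 = 23

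**Step 3: effect of the covariate.** Adjusted SD = 6.0 x sqrt(1 - rho²), which is 5.72, 5.20 and 4.28 at rho 0.3, 0.5 and 0.7. For a fixed sample size, the detectable difference scales by nearly the same factor whatever the true effect:
- rho 0.3: sqrt(0.91) = 0.954, about 5% smaller
- rho 0.5: sqrt(0.75) = 0.866, about 13% smaller, equivalent to 1/0.75 = 1.33 times the sample
- rho 0.7: sqrt(0.51) = 0.714, about 29% smaller, equivalent to 1/0.51 = 1.96 times the sample

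At 45 per arm and 80% power, the detectable difference is 3.58 episodes per week unadjusted, 3.10 at rho 0.5 and 2.56 at rho 0.7.

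**Step 4: illustrative power.** Noncentral t on dyad means, SD 6.0, one degree of freedom lost when adjusted. Gains in points are in brackets, taken before rounding.

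| Per arm | Difference | Unadjusted | rho 0.5 | rho 0.7 |
|---|---|---|---|---|
| 45 | 2.65 | 54.5% | 66.7% (+12.3) | 82.7% (+28.2) |
| 34 | 2.65 | 43.4% | 54.4% (+11.0) | 71.0% (+27.5) |
| 23 | 2.65 | 31.1% | 39.4% (+8.3) | 53.6% (+22.5) |
| 45 | 1.5 | 21.6% | 27.3% (+5.6) | 37.5% (+15.9) |
| 34 | 1.5 | 17.4% | 21.6% (+4.2) | 29.6% (+12.2) |
| 23 | 1.5 | 13.2% | 16.0% (+2.8) | 21.3% (+8.1) |
| 45 | 1.0 | 12.2% | 14.7% (+2.5) | 19.5% (+7.2) |
| 34 | 1.0 | 10.4% | 12.2% (+1.8) | 15.8% (+5.4) |
| 23 | 1.0 | 8.6% | 9.8% (+1.2) | 12.1% (+3.5) |

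At rho 0.3 the gain is at most 3.9 points (45 per arm, 2.65) and below 1 point for a difference of 1.0.

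These are two-group calculations on each dyad's mean. They approximate the GLMM and cover brushing only.

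**The case against.** The strongest objection is status. Section 6.1 describes the extension as a condition of the design that gives controls the same chance of rewards. The comparison is absent from the objectives and outcome measures in section 3, and the secondary hypotheses in 12.1 do not mention it. No power is claimed for it, so no stated figure is wrong. This stands, and it limits the importance of the point. It does not remove it: the protocol randomises these dyads and commits to comparing them.

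A second objection also stands in part. The covariate period is unrewarded and the outcome period is rewarded, so the change of regime could weaken rho.

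A reader might also infer more than the documents support:
- *That the plan throws away 12 to 28 points of power.* That range needs full uptake of an optional extension, a difference of 2.65 and rho of 0.5 to 0.7. None of these is documented for this comparison. Both arms have identical drawings, so the true difference could be well below 2.65.
- *That every control has a full year of brushing data.* Section 12.2 assumes 75% retention, and the counts depend on syncing. The baseline exists for controls who reach Month 12, possibly with gaps.
- *That the plan rules out adjustment.* Section 12.4 lists no covariates for any GLMM. It is silent, which is not exclusion.
- *That the unadjusted comparison is biased by chance imbalance.* Randomisation protects its validity, and its test already allows for chance imbalance.
- *That prior plaque is ignored.* Plaque is scored at Months 12 and 18, so the Month 12 score may enter the stated window as the first time point. The text does not say whether it would count as baseline or outcome.

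**Conclusion.** The point holds as a low-cost improvement to a secondary, unpowered comparison. No stated role is given to brushing before the second randomisation, although a suitable summary is already a defined outcome. The reduction in detectable difference (about 5%, 13% and 29% at rho 0.3, 0.5 and 0.7) depends only on rho, which the documents do not give. Power gains depend on uptake and the true difference as well, and should be reported only as a range. For rho 0.5 to 0.7, SD 6.0 and 23 to 45 per arm, they are about 8 to 28 points at a difference of 2.65, 3 to 16 at 1.5, and 1 to 7 at 1.0. Even with adjustment, the comparison stays weak for small differences. For plaque, what is needed is clarity on the role of the Month 12 score; no gain has been quantified there.

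**What to change.** Extend the communication-arm sentence in section 12.4 along these lines: *The Month 12-18 brushing models will include as a covariate the dyad's mean weekly count of qualifying half-day episodes between the Month 6 and Month 12 visits, computed from the available synced weeks. Missing covariate values will be imputed, so that no re-randomised dyad is dropped. For plaque, the Month 12 OHI-MIS score will be treated as a pre-randomisation baseline and not as a post-randomisation outcome.*

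Imputing the covariate from pre-Month 12 information only would keep it independent of the second allocation. If a power or precision statement is added, show it over a range of uptake, difference and rho.

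Cost: a short addition to the wording and one degree of freedom per model. No new data, visits or participants are needed.

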13 SOURCE DOCUMENTS AND ACCESS TO SOURCE DATA/DOCUMENTS

Study staff will maintain appropriate medical and research records for this study, in compliance with ICH E6, Section 4.9 and regulatory and institutional requirements for the protection of confidentiality of subjects. Study staff will permit authorized representatives of NIDCR and regulatory agencies to examine (and when required by applicable law, to copy) research records for the purposes of quality assurance reviews, audits, and evaluation of the study safety, progress and data validity.

Data collected in this study will take the form of toothbrushing data collected electronically via a Bluetooth-enabled toothbrush and a smartphone app, parent/caregiver drawing incentive data, parent/caregiver questionnaires administered in structured CAPIs, dental examination data, iPhone photographs of anterior teeth for OHI-MIS plaque score assessments, audio recordings from focus groups and interviews that will be transcribed, and cost data obtained from staff activity logs. FGDs and interviews will be digitally audiorecorded. Source documents for this study are: parent/caregiver questionnaires collected with electronic case report forms (eCRFs) during structured interviews, electronic smart toothbrushing performance data, digital photos of teeth saved as electronic image files, and dental examination data which will be collected electronically in REDCap. All data and source documents will be stored on password-protected computers with full hard drive encryption and secure servers behind a firewall.

Any paper informed consent forms administered if the electronic system is offline will be stored in locked cabinets.

14 QUALITY CONTROL AND QUALITY ASSURANCE

All staff will be appropriately trained in his/her position's duties with appropriate Human Subjects Research training; they will be provided with full information about the study such as background and significance, specific aims, milestones, study designs, procedures and analytic plans. All team members will be encouraged to view themselves as crucial team members encouraged to comment, ask questions, and make suggestions to ensure the highest study quality; robust and rigorous data will be gathered and handled according to protocol. Fidelity monitoring using audio recordings as described in Section 6.3 will help to ensure consistency when study staff explain intervention procedures and incentive program details to participants.

Working with the CC, we will use the REDCap web-based clinical trials management system (CTMS) to manage the trial visit schedule, group assignment, eCRFs, and AE and UP reporting. After training from the CC, staff will directly enter participant data into the CTMS.

Conventional EDC data-checking routines will assess data completeness and will ensure data are input successfully and within reasonable ranges. Checks will be done shortly after data collection. CC quality assessment reports will be provided to the team on a routine basis and will be reviewed regularly. After data-cleaning procedures, files for specific data collection will be validated and locked. Additionally, reports of electronic data collected will be provided to and reviewed with the study team for quality management purposes.

The study PIs will rigorously and periodically monitor study activities and engage in study team meetings to ensure that procedures are being performed correctly in the field in the proper sequence. If any breach is discovered, the particular activity will be undertaken a second time and monitored closely for full compliance with the approved procedures.

15 ETHICS/PROTECTION OF HUMAN SUBJECTS

15.1 Ethical Standard

The investigator will ensure that this study is conducted in full conformity with the principles set forth in The Belmont Report: Ethical Principles and Guidelines for the Protection of Human Subjects of Research, as drafted by the US National Commission for the Protection of Human Subjects of Biomedical and Behavioral Research (April 18, 1979) and codified in 45 CFR Part 46 and/or the ICH E6.

15.2 Institutional Review Board (IRB)

The protocol, informed consent form(s), recruitment materials, and all subject materials will be submitted to the IRB for review and approval. Approval of both the protocol and the consent form must be obtained before any subject is enrolled. Any amendment to the protocol, study procedures or instruments will require review and approval by the IRB before the changes are implemented in the study. UCSF's Committee on Human Research (CHR) will be the reviewing IRB while UCLA's CHR will be the relying IRB, formalized with an official Notice of Intent to Rely through the University of California system.

15.3 Informed Consent Process

Informed consent is a process that is initiated prior to the individual agreeing to participate in the study and continues throughout study participation. Discussion of risks and possible benefits of study participation will be provided to potential participants and their families. A consent form describing in detail the study procedures and risks will be given to the participant. Consent forms will be IRB-approved, and the participant is required to read and review the document on a digital tablet in English or Spanish or have the document read to him or her. The investigator or designee will explain the research study to the participant and answer any questions that may arise. The participant will electronically sign (with UCSF IRB-approved DocuSign) the informed consent document prior to any study-related assessments or procedures. Participants will be given the opportunity to discuss the study with their surrogates or think about it prior to agreeing to participate. They may withdraw consent at any time throughout the course of the study. A copy of the electronic signed informed consent document will be emailed to participants along with the Bill of Experimental Subject's Rights in English or Spanish (as per California law) for their records; participants who do not have email will be provided a paper copy of each. The rights and welfare of the subjects will be protected by emphasizing to them that the quality of their clinical care will not be adversely affected if they decline to participate in this study.

The consent process will be electronically documented in the clinical research record.

15.4 Exclusion of Women, Minorities, and Children (Special Populations)

Inclusion and exclusion criteria have been developed, which do not include any exclusions based on gender or race/ethnicity.

15.5 Subject Confidentiality

Subject confidentiality is strictly held in trust by the investigators, study staff, and the sponsor(s) and their agents.

The study protocol, documentation, data, and all other information generated will be held in strict confidence. No information concerning the study or the data will be released to any unauthorized third party without prior written approval of the sponsor.

Authorized representatives of the sponsor may inspect all study documents and records required to be maintained by the investigator for the study subjects. The clinical study site will permit access to such records.

No individual identities will be used in any reports or publications resulting from this study. No identifying information will be transmitted from the clinical site or UCSF to NIDCR.

eCRFs, which contain the participants' personal identifying information will be kept separately from other data.

